#### 6.5 Treatment compliance

The investigator or assigned staff will train the participant in the use of the medication, blood pressure monitor, and medication and blood pressure log. The participant will be instructed to record the number of study treatment capsules and/or tablets and antihypertensive combination therapy tablets taken during the study period.

At follow-up visits, participants will be instructed to return any unused treatment, and the accuracy of the medication diary will be verified by comparing the data entered with the amounts of study treatment returned. If any discrepancies are noted, the investigator/coordinator should discuss the discrepancy with the participant and document the detailed explanation in the study records.

#### 6.6 Concomitant treatment

The investigator should review each medication (prescribed or not) that the participant is receiving before starting the study and at each follow-up visit. Verification will be performed by asking the participant about any current or new medications they are using, and a respective interaction analysis will be performed so that the necessary actions can be taken to minimize the risk of response modification due to concomitant use with other medications. The investigator will inform the participant of the

Product: 910002

Importance of reporting new therapies or modifications in the use of current drugs for the proper conduct of research.

During the screening procedure, the patient's pharmacotherapy will be verified in order to identify drugs whose concomitant use may generate an interaction (defined in the Investigator's Manual) and which are defined as exclusion criteria.

#### 6.7 Treatment after completion of the study

No specific treatment is defined for after the end of the study. The investigator will inform the participant of the need to continue with their usual drug management as recommended by their treating physician.

#### 7.1 Loss of contact with the participant during follow-up

If the participant does not attend the research center for the required visits according to the schedule, the institutional instructions (I-INV-22: Follow-up of Lost Subjects in Clinical Research Studies) will be followed and the following activities will be carried out:

- The researcher/coordinator should attempt to contact the participant and schedule a missed visit. During contact with the participant, they should be advised on compliance with the instructions and controls required to ensure the proper conduct of the study.
- The investigator/coordinator should record the different strategies and attempts to contact the participant in the corresponding medical record.
- Evaluate the participant's withdrawal based on loss of contact and the participant's willingness to comply with the procedures defined in the protocol.

## 8 Study evaluations and procedures

### 8.1 General phases of execution

There are five phases for the execution of the clinical trial. The study procedures and the timing of their implementation are summarized in item 10 (Schedule of activities) and in Figure 2.

- **Recruitment:** Process of inviting volunteers to participate in clinical studies in areas where potential participants are concentrated (drug distribution centers, healthcare centers, etc.), identified among partner entities for the prioritization of strategies. The use of communication tools is proposed for the dissemination of the protocol, adherence tools or material, and the requirements for the recruitment of potential participants, which includes the selection criteria endorsed by the IRB according to institutional procedure (P-INV-24: Strategy for Recruitment, Selection, and Adherence of Volunteers for Clinical Research).
- **Screening:** Potential volunteers are identified and an initial approach is made. If a favorable response is obtained, the informed consent process for this phase is carried out, a participant identification card is issued, and medical assessment procedures, BMI, and sample collection for clinical laboratory analysis are performed.
- **Selection:** Based on the analysis of screening results, volunteers who meet the selection criteria established in this protocol will be identified and contacted. The first visit will be made, during which the researcher will talk to the potential participant, explaining the nature of the study, the requirements, and/or restrictions. Subsequently, the informed consent process for inclusion in the clinical study will be carried out, followed by the recording of general data and medical evaluation with initial recording of variables: sex, age, BMI, cardiovascular risk factors (family history of heart disease, hyperlipidemia, diabetes mellitus, abdominal obesity, smoking), comorbidities, previous treatment for HTN, concomitant medications, and laboratory results. At this stage, randomization is performed to define the study arm and corresponding medication dispensing according to sequence and delivery of follow-up items (digital blood pressure monitor, educational material, and daily log).
- **Follow-up of research volunteers:** The follow-up process will be carried out through visits every 4 weeks per medication studied (according to sequence 2 x 2). At visit 2 at the end of week 8, the study medication will be changed (group switch), and weeks 9 and 10 are identified as a statistical silence period. At the end of week 10, follow-up visit 3 will be carried out, in which the baseline conditions for medication B will be identified according to sequence, and follow-up visits 4 and 5 will then be carried out. During the follow-up visits, the schedule will be followed, with assessment by medicine, verification of adherence through counting of remaining medication units

Product: 910002

of medication remaining, verification of blood pressure readings, exploration of adverse events according to medical evaluation, and verification of laboratory results (Appendix 2). All information obtained during the visits will be recorded in the study CRF. Adverse event reports will follow the established institutional route for reporting to the Research Ethics Committee (REC) and relevant institutions, as appropriate.

- **Home monitoring:** Using the digital blood pressure monitor provided by the study (sponsor) and the recording material (diaries), the patient will take daily blood pressure measurements in the morning according to the procedure given by the doctor during the initial visit and reinforced during follow-up visits. The research volunteer will be instructed on the need to comply with recommendations regarding daily blood pressure measurements and recording them on the form designed for this purpose. In addition, warning signs will be reinforced for reporting and contacting the investigator during all visits. Reminder strategies will be implemented to ensure adherence to drug treatment and pharmacovigilance follow-up, such as messages and/or calls by the study coordinator on a weekly basis.
- **Study completion visit:** During weeks 19 and 20, study closure visits will be conducted, during which a final medical assessment will be performed.

During the study, the investigator is responsible for ensuring that procedures are performed by qualified and trained study personnel. The delegation of responsibilities of the study site personnel will be documented in the investigator's study folder.

All activities carried out during the selection process will be reviewed and recorded in the appropriate format to confirm compliance with eligibility criteria and documentation of basic information and reasons for non-selection.

The investigator may consider performing additional tests or evaluations for patient safety reasons, to be carried out in accordance with current regulations under good clinical practice criteria.

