**General design:**

Study phase	III
Clinical indication	Pharmacological management of essential hypertension
Population	Adults diagnosed with mild to moderate hypertension Mild to moderate

Product: 910002

Type of study	Intervention
Type of control	Active control
Study masking	Double-blind
Estimated study duration	The study is estimated to take 30 weeks from the time the first participant signs the informed consent form to the last study-related visit/call for the last participant. participant
Number of participants: It is proposed to recruit 50 volunteers	
Treatment groups and duration:	
Treatment groups	GROUP I: Administration of 30 mg extended-release Nifedipine Richmond for 8 weeks, followed by a change in treatment to comparator Nifedipine "according to the current medical formula" for 10 weeks (including 2 weeks of statistical silence). GROUP II: Administration of Nifedipine 30mg Extended Release Richmond for 8 weeks, followed by a switch to comparator Nifedipine "according to the current medical formula" for 10 weeks (including 2 weeks of statistical silence).
Duration of participation	Each volunteer will participate in the study for 20 weeks from the signing of the informed consent form for inclusion in the study until the final contact. The selection of patients who meet the selection criteria will be carried out during a 6-month enrollment period until the minimum sample size of 50 pairs, a total of 100 subjects in a crossover design (one patient = two study subjects), is reached. -Expected study start date: 2nd quarter of 2021 -Expected completion date : 4th quarter of 2021. During their participation, participants will receive antihypertensive medications (both nifedipine [comparator and study] and antihypertensive combination [unmodified]), a digital blood pressure monitor for home measurements, and a diary for recording medication intake and blood pressure readings.

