## 6.2 Treatment allocation method

Randomization/treatment assignment will be performed in permuted blocks at the research center by a person assigned and qualified for this activity who is not involved in the clinical evaluation of the participant, according to the following procedure (Figure 1):

- **Group A:** 8 weeks of treatment with Nifedipine Richmond New Formulation —  
-- 8 weeks of treatment with reference product (the first 2 weeks will be included for statistical silence).
- **Group B:** 8 weeks of treatment with reference product-----8 weeks of treatment with Nifedipine Richmond (the first 2 weeks will be included for statistical silence).

The random assignment method is by permuted blocks, where the random sequence will be taken between study groups A and B. The sequence will be carried out taking into account permutations 1. AB and 2. BA.

The random selection will use the random function (RANDOM: uniform distribution between 0 and 1) and the randomly selected sequence will be obtained using the equation  $\text{RANDOM} \times 2 + 1$ , taking the integer part; in the EXCEL Office 365 program.

**Table 2.** Random sequence list

Patient	Random	Randomx2+1	Sequence selected	Assigned sequence
1	0.67511186	2.350223724	2	BA
2	0.63655793	2.273115864	2	BA
3	0.82005771	2.640115417	2	BA

Product: 910002

4	0.75238537	2.504770731	2	BA
5	0.27060773	1.541215464	1	AB
6	0.13509461	1.27018922	1	AB
7	0.0059008	1.011801603	1	AB
8	0.00522046	1.01044092	1	AB
9	0.57459303	2.149186066	2	BA
10	0.13413163	1.268263257	1	AB
11	0.46855475	1.937109506	1	AB
12	0.43792582	1.875851646	1	AB
13	0.92905912	2.858118233	2	BA
14	0.76263057	2.525261134	2	BA
15	0.59039799	2.180795977	2	BA
16	0.67106409	2.342128183	2	BA
17	0.57513717	2.150274349	2	BA
18	0.95687127	2.91374253	2	BA
19	0.87915414	2.758308274	2	BA
20	0.51677593	2.033551866	2	BA
21	0.37768148	1.755362968	1	AB
22	0.13192216	1.263844313	1	AB
23	0.42201985	1.84403969	1	AB
24	0.20962522	1.419250439	1	AB
25	0.20456967	1.409139347	1	AB
26	0.65660156	2.313203122	2	BA
27	0.54821573	2.096431466	2	BA
28	0.91311981	2.826239619	2	BA
29	0.09187709	1.183754176	1	AB
30	0.66954146	2.339082914	2	BA
31	0.56996805	2.139936106	2	BA
32	0.35135826	1.702716511	1	AB
33	0.31718197	1.634363941	1	AB
34	0.42369607	1.84739214	1	AB
35	0.82200106	2.644002116	2	BA
36	0.50705857	2.014117148	2	BA
37	0.05075322	1.101506442	1	AB
38	0.03452872	1.069057445	1	AB
39	0.5778017	2.155603408	2	BA
40	0.74539157	2.490783148	2	BA

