#### 9.1 Summary of statistical analysis plan

Product: 910002

Design	Phase III, randomized, active-controlled clinical trial to evaluate the efficacy and safety of Nifedipine 30 mg extended-release in adult patients diagnosed with mild or moderate hypertension in Colombia.
Randomization	Permuted blocks, 1:1 ratio
Blinding	Double-blind
Analysis population	Efficacy assessment: Intention-to-treat (ITT) analysis Safety assessment: Analysis of patients treated (ASaT)
Criteria for Primary	Criteria
Secondary of assessment	Proportion of patients achieving the blood pressure control target (<140/90 mmHg) at week 4 of follow-up.  Proportion of patients experiencing serious and non-serious adverse events at week 8 of follow-up.
Statistical methods for efficacy analysis	Difference in mean SBP and DBP from baseline to weeks 4 and 8  Significance value and 95% CI for difference in mean SBP and DBP from baseline to 4 and 8 weeks between the two treatments (repeated measures ANOVA).  p-value or significance value and 95% CI for differences between the proportions of normal blood pressure readings (<140/90 mmHg) at 4 and 8 weeks between treatments using McNemar's chi-square test for differences in proportions with and without continuity correction or Fisher's exact test for paired designs (expected values < 5).
Statistical methods for safety analysis	Percentage of serious and non-serious adverse events between treatments and percentage by type of adverse event for each treatment (descriptive).
Size and power of the sample	A sample size of 50 patients is defined, each patient = 2 study subjects.

Product: 910002

For a maximum change of 3 mmHg between the two treatments, with 90% power, 95% reliability, and 10% losses, a 1:1 ratio, and a sample size of 50:50 (1 patient = 2 study subjects).

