Screening week (SW): identification of recruitment sites, communications logistics, selection criteria (inclusion/exclusion), medical history, review of pharmacotherapeutic profile (history/concomitant medications), Identification and approach to patients with Nifedipine, presentation of research protocol, verification of selection criteria, informed consent process, medical evolution, verification of signs and symptoms, clinical laboratory and electrocardiogram.																						
S1: Initial visit, participant inclusion, medical assessment, BP verification, therapeutic education, medical education, reading of paraclinical tests, pregnancy test (2), monitoring of adverse events. A pregnancy test is taken during the screening week and prior to administration of the medication due to possible hormonal changes.																						
S2: Reminder strategy, monitoring of adverse events by telephone call from the CAIMED study team within a 5-day window.																						
S5: Visit 1, corresponding to four weeks after dispensing the medication, medical assessment, BP check, therapeutic education, clinical laboratory tests, pregnancy test, electrocardiogram, monitoring of adverse events, dispensing of medication, monitoring of adverse events, and BP logbook. Verification of adherence																						

Product: 910002

S6: During this week, the paraclinical tests taken in week five will be verified. If the patient shows any abnormalities, the study physician will contact the patient.	
S9: Visit 2, corresponding to four weeks after dispensing the medication, medical assessment, BP check, therapeutic education, clinical laboratory tests, pregnancy test, electrocardiogram, monitoring of adverse events, dispensing of medication, monitoring of adverse events, and BP logbook. Verification of adherence	
S10: Reminder strategy, monitoring of adverse events by telephone call from the CALMED study team within a 5-day window. During that week, the paraclinical tests taken in week nine will be verified, and if the patient shows any abnormalities, the study physician will contact the patient.	
S11: Visit 3: Follow-up visit 3 will be conducted to verify the baseline conditions for medication B according to the sequence. During this visit, a medical assessment, BP check, therapeutic education, clinical laboratory tests, pregnancy test, electrocardiogram, monitoring of adverse events, BP logbook, and adherence verification will be performed.	

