S12: During this week, the paraclinical tests taken in week five will be verified. If the patient presents any abnormalities, the study physician will contact the patient.	
S15: Visit 4: corresponds to four weeks after dispensing medication B, medical assessment, BP check, therapeutic education, clinical laboratory tests, pregnancy test, electrocardiogram, monitoring of adverse events, medication dispensing, monitoring of adverse events, and BP logbook. Adherence check	
S16: During this week, the paraclinical tests taken in week five will be verified. If the patient shows any abnormalities, the study physician will contact the patient.	
S19: Visit 5: medical assessment, BP check, therapeutic education, clinical laboratory tests, pregnancy test, electrocardiogram, monitoring of adverse events, adherence check	
S20: During this week, the paraclinical tests taken in week five will be verified. If the patient presents any abnormalities, the study physician will contact the patient. CLOSING	

Product: 910002

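### The visit named as baseline for the second drug falls two weeks into that drug; used in change-from-baseline comparisons of mean blood pressure, it would shrink the contrast if most of the switch effect is present by then

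*Protocol*

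**What the plan says.** Section 8.1 sets the switch at the second follow-up visit, after eight weeks on the first drug: "the study medication will be changed (group switch), and weeks 9 and 10 are identified as a statistical silence period". Section 6.2 shows that these silence weeks are not drug-free. For the group that starts on the reference product, the second period is "8 weeks of treatment with Nifedipine Richmond (the first 2 weeks will be included for statistical silence", and the other group has the mirror arrangement. Section 8.1 then describes visit 3: "At the end of week 10, follow-up visit 3 will be carried out, in which the baseline conditions for medication B will be identified". Section 8.4 repeats this, and the notes to the schedule in section 13 say the same for S11: "Follow-up visit 3 will be conducted to verify the baseline conditions for medication B according to the sequence". The period-1 baseline is S1, before the first randomised dose, in patients who already use nifedipine (section 5.1).

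The efficacy methods in section 9.1 include "Difference in mean SBP and DBP from baseline to weeks 4 and 8", compared between treatments by repeated measures ANOVA. Section 4.4.1 lists the same changes as an endpoint. Section 9.5.1.1, headed as the primary efficacy analysis, compares mean SBP and DBP before and after the intervention, and also tests control proportions with McNemar's test. The named primary endpoint (sections 3.1 and 9.3.1) is the proportion below 140/90 mmHg at week 8. The sample size (section 4.2.1) rests on mean pressure: margin 3 mmHg, SD of the difference 6 mmHg, one-sided 2.5%, 90% power, 44 pairs.

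**The concern.** A baseline taken after two weeks on a drug already contains part of that drug's effect. In period 2, the change from such a baseline largely compares the second drug with itself. In period 1, the change runs from pre-study nifedipine to the first randomised product. The two changes are different quantities, and pooling them can dilute the contrast between the products. In a non-inferiority trial, dilution towards zero favours the test product: a Richmond formulation that is worse by the full margin could look acceptable.

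The visit labels add to the problem. The S15 note in section 13 says that the visit "corresponds to four weeks after dispensing medication B", but the grid shows dispensing at S9 and none at S11, so S15 is six weeks after dispensing and S19 is ten. The period-2 readings labelled weeks 4 and 8 would then be taken at weeks 6 and 10 of exposure.

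**Working it through.** **Reproducing the plan's figure.** n = (SD × (z0.975 + z0.90) / margin)² = (6 × 3.2415 / 3)² = 42.03, so 43 by the normal approximation. The exact paired t calculation gives power 0.900 at n = 44, which is the plan's number. For losses, 44 / 0.9 = 48.9, so 49 against the stated 50. The sample size therefore describes a paired comparison of mean pressure at the 3 mmHg margin.

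**Expected contrast of change scores.** Let R and C be the mean pressures on Richmond and on the comparator, b the pre-study level, and tau = R - C (positive means Richmond is worse). Let f be the share of the switch effect present at S11.

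| Sequence | Period-1 change (S9 - S1) | S11 reading | Period-2 change (S19 - S11) |
|---|---|---|---|
| Richmond then comparator | R - b | fC + (1 - f)R | -(1 - f)tau |
| Comparator then Richmond | C - b | fR + (1 - f)C | +(1 - f)tau |

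- Period-1 contrast, Richmond minus comparator: tau.
- Period-2 contrast: 2(1 - f)tau.
- Period-adjusted estimate, the mean of the two: (1.5 - f)tau.

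The pre-study level cancels in this equally weighted estimate. It would not cancel in an unadjusted paired mean, because Table 2 in section 6.2 allocates 22 patients to AB and 28 to BA.

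**Effect on the non-inferiority decision.** With k = 1.5 - f and a true difference equal to the 3 mmHg margin, P(declare non-inferiority) = Phi((3 - 3k)/SE - 1.96). With 44 pairs, SE = 6/√44 = 0.905 if the SD of 6 also applies to differences of changes. If change scores have twice the variance (independent errors at each visit), the SD is 6 × √2 = 8.49 and SE = 1.279. The documents do not give f, so a range is shown.

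| f (assumed) | Factor k | True 3 mmHg appears as | False non-inferiority, SD 6 | False non-inferiority, SD 8.49 |
|---|---|---|---|---|
| 1 | 0.5 | 1.5 | 38% | 22% |
| 0.9 | 0.6 | 1.8 | 26% | 15% |
| 0.8 | 0.7 | 2.1 | 17% | 10% |
| 0.5 | 1.0 | 3.0 | 2.5% | 2.5% |

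A simulation of 6,000 trials per setting, with independent visit errors, agrees. At f = 1 with 44 patients the mean estimate was 1.50 for a true 3.0, with 20% false non-inferiority by the t-based limit. At f = 0.8 with 50 patients it was 2.12, with 10%.

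**Alternatives.** Comparing raw end-of-period values gave 3.00 for a true 3.0, with a 2.3% error rate (44 patients). A single S1 baseline for both periods gives the same result, because it cancels within the patient. Using the week-8 switch reading as the period-2 baseline does not help: that reading is on the other product, so f = 0 and the factor is 1.5 (simulated 4.49 for a true 3.0, 50 patients).

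**The case against.** Several points on the other side have weight.

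- **Primary endpoint.** A reader might infer that the trial's primary result is biased. The documents do not support that. The named primary endpoint is control status at week 8, tested by McNemar, and it uses no baseline. A Grizzle two-period model, which section 9.5.1.1 also names, is equally unaffected if fitted to raw end-of-period values. What remains is that mean pressure stands under the primary analysis heading and is the only basis of the sample size.
- **Link to the change score.** Sections 4.4.1 and 9.1 say from baseline without naming a visit, and no section says that the S11 reading is subtracted. The link is an inference. It is the natural one, because visit 3 is the only baseline the protocol names for the second drug.
- **Size.** A reader might infer that any true difference is always halved. That is the f = 1 case only. Treating the first two weeks as a silence period suggests that the switch effect is expected to be largely complete by then, but it does not establish f = 1. At f = 0.5 there is no bias, and below that the difference is exaggerated.
- **Power.** A reader might also infer that power falls from 90% to about 63%. That follows with an SD of 8.49 and 44 pairs, but only if the stated SD of 6 refers to raw end-of-period differences and visit errors are independent. The protocol settles neither.

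**Conclusion.** The concern holds in conditional form. The protocol calls a reading taken two weeks into the second drug its baseline, and lists change from baseline among the efficacy comparisons. If the two are combined, the period-adjusted contrast is (1.5 - f) times the true difference. For f between 0.8 and 1, an assumption, a true 3 mmHg deficit would appear as 2.1 to 1.5 mmHg, and the error rate at the margin would be roughly 10% to 38%, depending on f and on the SD of change scores. The result rests on the period-adjusted estimator, on 44 evaluable pairs, and on S11 being the baseline used. The week-8 responder comparison and any analysis of raw end-of-period pressure stand as they are. Leaving the baseline visit unstated is no safeguard, because the reading at the switch would also give a wrong answer.

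Three inconsistencies around this visit are in the text whatever f may be: the S15 label against dispensing at S9; a second period of 8 weeks including the silence in section 6.2 against one "for 10 weeks (including 2 weeks of statistical silence" in the synopsis; and a blood pressure check at S11 in the schedule notes that the grid does not mark.

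**What to change.** State in sections 4.4.1, 8.1 (with the matching text in 8.4) and 9 that mean SBP and DBP are compared directly on end-of-period values, S9 for period 1 and S19 for period 2, in a model with treatment, period and sequence as fixed effects and patient as random effect. State that the S11 reading is reported only as a week-2 on-drug value and is not used as a baseline. Label the period-2 visits by actual weeks on the second drug. Reconcile the passages on dispensing and the S15 label, on the length of period 2, and on whether blood pressure is measured at S11.

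The cost is a wording amendment. The comparison needs no added visits, patients or measurements, since the grid already marks blood pressure at S9 and S19. Section 9 sends changes of analysis method made during the study and before unblinding through a protocol amendment, so it should be made by that route.
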